## 2.1 Study Rationale

One of the major mechanisms for resistance to EGFR-TKIs is amplification of the MET receptor tyrosine kinase, which activates downstream intracellular signalling independent of EGFR. This study will explore the individual contribution of savolitinib to MET-mediated osimertinib resistance.

This study will analyse the individual contribution of savolitinib to the combination by investigating the efficacy of the combination versus savolitinib plus placebo in patients with EGFRm+ and MET amplified, locally advanced or metastatic NSCLC who have progressed

following treatment with osimertinib.

The rationale for the design of the study is presented in Section 4.2.

## **2.2 Background**

Refer to Section 2.

A detailed description of the chemistry, pharmacology, efficacy, and safety of savolitinib and osimertinib is provided in their respective IBs.

## **2.3 Benefit/Risk Assessment**

More detailed information about the known and expected benefits and potential risks of savolitinib and osimertinib may be found in their respective IBs.

### **2.3.1 Risk Assessment**

Investigators for a study using savolitinib monotherapy in patients with EGFRm+ NSCLC will be cognisant of the potential risk of rapid disease progression via EGFRm tumour driver reactivation. The NCCN Guidelines for NSCLC (NCCN 2020) include a warning about the risk of flare phenomenon occurring in patients who discontinue EGFR-TKI. Tumour flare after discontinuation of EGFR-TKI has been a recognised phenomenon for many years (Chaft et al 2011; Chen et al 2013) and indicates that the EGFRm sensitising mutation is not eliminated from the tumour following treatment with an EGFR-TKI in most patients. In some patients, this may cause a rapid clinical deterioration after discontinuing EGFR-TKI prior to entering the study (see Section 4.2.1). To minimise this risk, patients will be closely monitored over the first month of participation in the study to look for evidence of tumour flare. At investigator-assessed PD per RECIST 1.1, treatment allocation will be unblinded and those patients randomised to the savolitinib plus placebo arm will have the opportunity to cross-over to the savolitinib plus osimertinib regimen. Patients will be informed of the possibility of cross-over to savolitinib plus osimertinib during the informed consent process and at the time of progression on randomised treatment. Further risks and the respective mitigation steps are presented in Table 3.

**Table 3 Risk Assessment**

Potential risk of clinical significance	Summary of data/rational for risk	Mitigation strategy
Study intervention: osimertinib a		
Interstitial lung disease	Interstitial lung disease or ILD-like adverse reactions were reported in 3.9% of patients in the osimertinib pivotal clinical studies dataset, with 1.1% of these being severe (CTCAE Grade 3 or 4) and 0.4% resulted in a fatal outcome.	Patients with past or clinically active ILD will be excluded. Specific guidance on dose modification to manage new or worsening pulmonary symptoms is included in this CSP. See Section 5.2 and Appendix I 2.1
QTc interval prolongation	In the osimertinib clinical studies dataset 0.9% of patients were reported to have a QTc greater than 500 msec and 3.6% of patients had an increase from baseline QTc greater than 60 msec.	Patients with cardiac diseases and restriction of drugs known to prolong QT interval will be excluded. Regular cardiac monitoring through ECGs has also been included in the SoAs. Specific guidance on dose modification in the event of QTc interval prolongation has been included in this CSP. See Table 1, Table 2, Sections 5.2 and 6.5, and Appendix I 1.1
Keratitis	In the osimertinib clinical studies dataset 0.7% of patients were reported to have signs or symptoms suggestive of keratitis.	Physical examinations, which include assessments of the patient's eyes will be completed at every visit. Patients presenting with signs or symptoms suggestive of keratitis will be promptly referred to an ophthalmologist. See Section 8.2.1 and Appendix I 2.2
Erythema multiforme and Stevens-Johnson syndrome	Case reports of EM and SJS have been uncommonly and rarely reported, respectively, in association with osimertinib treatment.	Before initiating treatment, patients will be advised of the signs and symptoms of EM and SJS. Physical examinations, which include assessments of the patient's skin will be completed at every visit. Specific guidance on dose modification in the event of the EM or SJS has been included in this CSP. See Section 8.2.1 and Appendix I 1.1
Changes in cardiac contractility	Left ventricular ejection fraction decreases $\geq 10$ percentage points and a drop to less than 50% occurred in 3.9% of patients who had baseline and at least 1 follow-up LVEF assessment (N = 908).	Patients with cardiac diseases will be excluded. Regular cardiac monitoring through ECHO/MUGA scans has also been included in the SoAs. Specific guidance on dose modification in the event of changes in cardiac contractility has been included in this CSP. See Table 1, Table 2, Section 5.2 and Appendix I 2.3

**Table 3 Risk Assessment**

Potential risk of clinical significance	Summary of data/rational for risk	Mitigation strategy
Study intervention: savolitinibb		
Hepatotoxicity	Hepatotoxicity (AEs within standardised MedDRA query of Drug-induced hepatic disorders): was reported in 35.0% of patients, of which 4.8% were reported as serious. In total, 11.5% of patients had an AE of hepatotoxicity CTCAE Grade $\geq$ 3.	Patients with increased liver enzymes will be excluded. Restrictions on the use of concomitant medications that are known to effect the liver, ie, paracetamol/acetaminophen and statins have also been included. Regular LFTs and specific guidance on dose modification in the event of hepatotoxicity have been included in this CSP. See Table 1 , Table 2 , Sections 5.1 , 5.2 , and 6.5 and Appendix I 3.2
SJS	A cumulative search in the AstraZeneca’s global Patient Safety database for savolitinib using the preferred terms of SJS, toxic epidermal necrolysis and EM retrieved 1 case of SJS.	Patients who show symptoms or signs suggesting emerging SJS while on study treatment (eg, progressive skin rash often with blisters or mucosal lesions), must discontinue savolitinib immediately and receive appropriate treatment. If emerging SJS is suspected, re-challenge with savolitinib must be avoided. See Section 8.2.1 and Appendix I 3.3
Hypersensitivity	Cumulatively to date, 22 SAEs of drug hypersensitivity have been received, including anaphylaxis, of which 17 occurred in Study D5160C00006 (TATTON), which studied the combination of osimertinib and savolitinib.	Specific guidance for the management of hypersensitivity has been included in the CSP. CCI [REDACTED] See Appendix I 3.3
QTc prolongation	Electrocardiogram QT prolonged was reported as an AE in 1.2% of patients in the savolitinib clinical database.	See above for mitigation strategy. See Table 1 , Table 2 , Sections 5.2 and 6.5 , and Appendix I 3.3

**Table 3 Risk Assessment**

Potential risk of clinical significance	Summary of data/rational for risk	Mitigation strategy
Study procedures		
Biopsies	Risks from biopsies include pain, bleeding, infection and accidental injury to nearby tissues. There is also a risk associated when anaesthetic is required.	New biopsies should only be taken specifically for Pre-screening for this study where the expected risk of an AE related to the procedure is < 2%. High-risk sites such as the brain and pancreas should be avoided. See Table 1 , and Section 8.6

a Incidences of AEs reported for osimertinib are from the osimertinib pivotal clinical studies dataset, which is comprised of 1142 patients who received osimertinib monotherapy for NSCLC in AURA (Study D5160C00001) and FLAURA (Study D5160C00007) and includes data up to the DCO of 12 November 2019.

b Incidences of AEs reported for savolitinib are from the clinical database, which includes 643 patients from Studies D5081C00001, D5081C00002, D5082C00002, D5081C00003, D5160C00006, D5081C00004, D5080C00001, D5084C00001 and D5081C00013 and includes data up to the DCO of 26 February 2019.

AE = Adverse events; CTCAE = Common Terminology Criteria for Adverse Events; CSP = Clinical study protocol; DCO = Data cut-off;  
ECG = Electrocardiogram; ECHO = Echocardiogram; EM = Erythema multiforme; **CCI** ██████████ ILD = Interstitial lung disease; LFT = Liver function test; LVEF = Left ventricular ejection fraction; MedDRA = Medical Dictionary for Regulatory Activities; MUGA = Multi-gated acquisition; NSCLC = Non-small cell lung cancer; QTc = corrected QT interval; SAE = Serious adverse events; SoAs = Schedule of activities; SJS = Stevens-Johnson syndrome.

### **2.3.2 Benefit Assessment**

Savolitinib has the potential to be active against a wide range of tumour types and is currently being assessed in Phase I, II and III of clinical development for solid tumours (including NSCLC) as monotherapy or in combination therapy with osimertinib.

Osimertinib has an established efficacy profile with proven effectiveness in adult patients with locally advanced or metastatic EGFR T790M mutation-positive NSCLC whose disease has progressed on or after EGFR-TKI therapy and as a first-line treatment of patients with locally advanced or metastatic NSCLC whose tumours have EGFR exon 19 deletions or exon 21 (L858R) substitution mutation. In addition, osimertinib has a well-established safety profile that is similar in both populations.

AstraZeneca believes the investigation of savolitinib and osimertinib in patients with advanced NSCLC appears acceptable based upon: the non-clinical safety profile, the emerging clinical safety profile, the risk minimisation and AE management proposals, early evidence of activity in patients with advanced cancer, the limited life expectancy due to malignant disease, the lack of effective alternative treatments, and the strength of the scientific hypothesis under evaluation.

In addition to the potential benefits from study intervention, patients will also benefit from access to medical care with regular disease assessments.

### **2.3.3 Overall Benefit: Risk Conclusion**

[figure not shown]
Overall the benefit/risk assessment supports the further investigation of savolitinib and osimertinib in patients with locally advanced or metastatic NSCLC based upon: the non-clinical safety profile, the emerging clinical safety profile, the risk minimisation, including close monitoring for tumour flare over the first month on study, AE management proposals, the study design, the limited life expectancy due to malignant disease, the lack of effective alternative treatments, the strength of the scientific hypothesis under evaluation, and the safety and efficacy data from TATTON.

### 3 OBJECTIVES AND ENDPOINTS

**Table 4 Objectives and Endpoints**

Objectives	Endpoints
Primary	
To assess the ORR of savolitinib in combination with osimertinib versus savolitinib in combination with placebo in patients with EGFRm+, MET amplified locally advanced or metastatic NSCLC who have progressed on previous osimertinib therapy	Objective response rate is defined as the proportion of patients with measurable disease who have a CR or PR as determined by the investigator at the local site per RECIST 1.1.
Secondary	
To determine the efficacy of savolitinib in combination with osimertinib versus savolitinib in combination with placebo in patients with EGFRm+, MET amplified locally advanced or metastatic NSCLC who have progressed on previous osimertinib therapy	
 
• Progression-free survival is defined as time from randomisation until progression per RECIST 1.1 as assessed by the investigator or death due to any cause.
 
• Duration of response is defined as the time from the date of first documented response until date of documented progression per RECIST 1.1 as assessed by the investigator or death in the absence of disease progression.
 
• Tumour size assessment is defined as the percentage change from baseline in TLs at 12 weeks per RECIST 1.1 as assessed by the investigator.
 
• Overall survival is defined as time from randomisation until the date of death due to any cause.
 

To evaluate the efficacy of savolitinib plus osimertinib in patients who cross-over after progression on savolitinib plus placebo a	
 
• Objective response rate is defined as the proportion of patients with measurable disease who have a CR or PR as determined by the investigator at the local site per RECIST 1.1.
 
• Progression-free survival is defined as time from the first dose in the cross-over period until progression per RECIST 1.1 as assessed by the investigator or death due to any cause.
 
• Duration of response is defined as the time from the date of first documented response during the cross-over period until date of documented progression per RECIST 1.1 as assessed by the investigator or death in the absence of disease progression.
 
• Tumour size assessment is defined as the percentage change from baseline in TLs at 12 weeks per RECIST 1.1 as assessed by the investigator.
 

To evaluate the PK of savolitinib and osimertinib.	Plasma concentrations of savolitinib, osimertinib, and their metabolites.

**Table 4 Objectives and Endpoints**

Objectives	Endpoints
To determine the prevalence of ctDNA clearance after savolitinib plus osimertinib or savolitinib plus placebo treatment in this patient population.	Total clearance in EGFR mutations at 6-weeks after therapy initiation (percentage and absolute change from baseline in EGFR mutation allele frequencies).
Safety	
To evaluate the safety and tolerability of savolitinib plus osimertinib or savolitinib plus placebo.	Safety and tolerability will be evaluated in terms of AEs, SAEs and discontinuation rate due to AEs. Clinical chemistry/haematology including LFTs. ECHOs, ECGs and vital signs including blood pressure and heart rate.
Tertiary/Exploratory	

CCI
 	

a Baseline for ORR, PFS, DoR and tumour size assessments of patients who cross-over to savolitinib plus osimertinib from savolitinib plus placebo will be the progression scan on savolitinib plus placebo acquired within 28 days of the start of treatment in the cross-over period.

CCI

AE = Adverse event; CR = Complete response; CCI [redacted] ctDNA = Circulating tumour DNA; DoR = Duration of response; ECG = Electrocardiogram; ECHO = Echocardiogram; EGFR = Epidermal growth factor; EGFRm+ = Epidermal growth factor receptor mutation positive; CCI [redacted] LFT = Liver function test; MET = Hepatocyte growth factor receptor; NSCLC = Non-small cell lung cancer; ORR = Objective response rate; CCI [redacted] PFS = Progression-free survival; PK = Pharmacokinetics; PR = Partial response; RECIST = Response Evaluation Criteria in Solid Tumours; SAE = Serious adverse events; TL = Target lesion.

## 4 STUDY DESIGN

### 4.1 Overall Design

This is a multi-centre, Phase II, double-blind, randomised study designed to determine the efficacy of savolitinib administered orally in combination with osimertinib versus savolitinib in combination with placebo in patients with EGFRm+, MET amplified, locally advanced or metastatic NSCLC who have progressed on previous osimertinib treatment.

For an overview of the study design see [Figure 1](#) and [Section 1.3](#). For details on treatments given during the study, see [Section 6.1](#).

For details on what is included in the efficacy and safety endpoints, see [Section 3](#).

#### 4.1.1 Randomised Study Design

Prior to CSP V3.0, approximately 56 patients were planned to be randomised in a ratio of 1:1 to receive treatment with CCI savolitinib CCI plus CCI osimertinib CCI or CCI savolitinib CCI plus placebo. At least half of the patients randomised into the study will be second-line patients who were treated with osimertinib as first-line therapy. Randomisation will be stratified according to the number of prior lines of therapy (ie, osimertinib monotherapy as first line or  $\geq$  second line [which includes patients who received osimertinib monotherapy before or after chemotherapy]).

Prospective testing of tumour specimens to determine MET amplification by central FISH using tumour specimens collected after progression on prior treatment with osimertinib should be performed at Pre-screening in advance of Screening for the main study. Patients determined to be MET amplified in Pre-screening will undergo screening during the 28 days prior to randomisation to confirm eligibility ([Sections 5.1](#) and [5.2](#)).

Provision of a FFPE tumour specimen is mandatory (refer to the Laboratory Manual for detailed specimen requirements). This will be used for prospective analysis of MET amplification by FISH.

Patients will continue to receive study medication CCI in 28-day cycles until objective PD by RECIST 1.1 is assessed, unacceptable toxicity occurs, consent is withdrawn or another discontinuation criteria is met ([Section 7](#)). At the time of investigator assessment per RECIST 1.1 of PD, the randomisation blind can be broken and patients who were initially randomised to the savolitinib plus placebo arm will be given the opportunity to cross-over (see [Sections 4.1.2](#) and [6.3](#)). Patients originally randomised to savolitinib plus osimertinib may continue to receive treatment with savolitinib plus osimertinib or osimertinib monotherapy (if savolitinib was stopped earlier) beyond RECIST 1.1 defined PD as long as they continue to receive clinical benefit, in the opinion of the investigator, and do not meet any of the

discontinuation criteria. No other anti-cancer agent is permitted in combination with osimertinib within this study. Patients can continue on savolitinib monotherapy (if randomised to the savolitinib plus placebo arm or if osimertinib was stopped earlier) until objective PD by RECIST 1.1 is assessed. Savolitinib monotherapy post-progression is not permitted.

Prior to CSP V3.0, a non-comparative interim futility analysis for the savolitinib plus placebo arm was planned to occur after 20 patients overall (10 per arm) had the opportunity of being treated for 2 RECIST post-baseline scans (12 weeks; Section 9.5). Recruitment was to continue during this interim futility analysis. The primary analysis was planned to occur 6 months after the last patient had been randomised. The final analysis was planned to be performed after the earlier of 18 months after the last patient was randomised or when 70% of the patients had progressed or died due to any cause.

Under CSP V3.0, as a result of AstraZeneca's decision to terminate study recruitment early, the planned number of randomised patients will not be met, and the planned interim futility analysis and primary analysis will not be performed. Alternatively, an early review of the data by AstraZeneca will occur following the early termination of study recruitment. The final analysis will be performed following the final DCO, which will take place 9 months after the last patient has been randomised. CCI [REDACTED]

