- e Liver function tests will be performed weekly for the first 10 weeks from randomisation, then Day 1 of every subsequent cycle and at progression. Where a liver function test is the only assessment, a clinic visit is not required as the test may be performed offsite. In the case of elevated liver function tests, please refer to Appendix I 3.2 for enhanced monitoring and management procedures.

CCI

- h For patients who cross-over based on confirmed objective disease progression during the initial randomised treatment period (including patients who have already crossed over based on confirmed PD prior to CSP Version 3.0), scheduled RECIST 1.1 tumour assessments are not required, and the subsequent assessment of disease progression will be based on standard-of-care scan or investigator determined clinical progression. Scheduled RECIST 1.1 tumour assessments are required (the scan frequency is against initial randomisation) for patients who cross-over after study unblinding and who have not objectively progressed during the initial randomised treatment period. Patients who cross-over after study unblinding, who have no objective progression during initial randomisation period, and who discontinue study intervention after cross-over for reasons other than investigator-confirmed disease progression will continue scheduled RECIST 1.1 tumour assessments until objective disease progression per RECIST 1.1 as assessed by investigator, unless they withdraw consent to the entire study. At the same time points, vital signs, ECGs and plasma samples for ctDNA will be collected. Serious adverse events considered related to study intervention and/or study procedures will be collected throughout progression follow-up.
- i Patients who cross-over must not receive any other anti-cancer therapies between the assessment of PD and the addition of osimertinib. Savolitinib treatment should continue uninterrupted during this period.
- j Patients will be contacted for survival follow-up Q12W. Patients should be contacted in the week after data cut-off for each study analysis to establish survival status. Serious adverse events considered related to study intervention will be collected throughout survival follow-up.

Note: For patients continuing in the study after final DCO, refer to Section 6.7 for required activities.

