#### **4.1.2 Cross-over Study Design**

Patients randomised to the savolitinib plus placebo arm may cross-over to open-label savolitinib plus osimertinib following investigator-assessment of PD per RECIST 1.1 to ensure that all patients enrolled may have the opportunity to receive the combination of savolitinib plus osimertinib. Patients will be informed of the possibility of cross-over to savolitinib plus osimertinib during the informed consent process and at the time of progression on randomised treatment. A separate ICF for cross-over patients must be signed prior to starting cross-over treatment.

Patients who cross-over must not receive any other anti-cancer therapies between the assessment of PD and the addition of osimertinib. Savolitinib treatment should continue uninterrupted during this period. Patients should be crossed over as soon as possible after the assessment of PD and within 28 days of their progression scan.

Patients who cross-over will receive study medication CCI [REDACTED] in 28-day cycles until occurrence of investigator-assessed objective PD, unacceptable toxicity occurs, consent is withdrawn or another discontinuation criteria is met. As in the randomised part of the study, patients may continue to receive treatment with osimertinib plus savolitinib or osimertinib monotherapy (if savolitinib is stopped during cross-over because of savolitinib-related toxicity) beyond RECIST 1.1 defined PD as long as they continue to receive clinical benefit, in the opinion of the investigator, and do not meet any of the discontinuation criteria. No other

anti-cancer agent is permitted in combination with osimertinib within this study.

Prior to CSP V3.0, if after the planned interim futility analysis (see Section 9.5) the study was declared futile and a recommendation to stop the study was made by the IDMC, there was to be a database lock, followed by the usual end of study reporting activities.

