The randomisation code can be broken after investigator-assessed PD per RECIST 1.1. Patients initially randomised to the savolitinib plus placebo arm may then be offered the opportunity to cross-over to receive savolitinib in combination with osimertinib. Once the investigator has documented progression in the eCRF, and obtained approval for unblinding from the study physician, the treatment code for a patient may be obtained from the IWRS via a dedicated option they may select in this situation. In all other circumstances the randomisation code should not be broken except in medical emergencies when the appropriate management of the patient requires knowledge of the treatment randomisation. The investigator documents and reports the action to AstraZeneca, without revealing the treatment given to the patient to the AstraZeneca staff.

AstraZeneca retains the right to break the code for SAEs that are unexpected and are suspected to be causally related to an investigational product and that potentially require expedited reporting to regulatory authorities. Randomisation codes will not be broken for the planned analyses of data until all decisions on the evaluability of the data from each individual patient have been made and documented.

The IWRS/IWRS will be programmed with blind-breaking instructions. In case of an emergency, in which the knowledge of the specific blinded study intervention will affect the immediate management of the patient's condition (eg, antidote available), the investigator has the sole responsibility for determining if unblinding of a patients' intervention assignment is warranted. Patient safety must always be the first consideration in making such a determination. If a patient's intervention assignment is unblinded, the sponsor must be notified within 24 hours after breaking the blind. The investigator documents and reports the action to AstraZeneca, without revealing the treatment given to the patient to the AstraZeneca staff. Additionally, patients with investigator-assessed objective PD may be unblinded.

Prior to CSP V3.0, the AstraZeneca study team was to be unblinded at the time of the primary analysis. Under CSP V3.0, following the early termination of study recruitment, an initial DCO will occur to allow an early review of the data. The study will be unblinded after data cleaning activities on this initial DCO data have been completed.

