## **7 DISCONTINUATION OF STUDY INTERVENTION AND PATIENT DISCONTINUATION/WITHDRAWAL**

### **7.1 Discontinuation of Study Intervention**

It may be necessary for a patient to permanently discontinue (definitive discontinuation) study intervention. If study intervention is permanently discontinued, the patient will remain in the study to be evaluated for survival.

Patients may be discontinued from study intervention in the following situations. Note that discontinuation from study intervention is NOT the same thing as a withdrawal from the study.

- Patient decision. The patient is at any time free to discontinue treatment, without prejudice to further treatment.
- Adverse events.
- Severe non-compliance with the CSP.
- Disease progression as per RECIST 1.1; unless the patient is randomised to savolitinib plus placebo, when cross-over to savolitinib plus osimertinib may be permitted.

- Patients incorrectly initiated on study medication.
- Pregnancy.
- Specific stopping criteria, ie, ILD, acute anaphylaxis or QTcF interval prolongation with signs/symptoms of serious arrhythmia.

See the SoAs ([Table 1](#) and [Table 2](#)) for data to be collected at the time of intervention discontinuation and follow-up and for any further evaluations that need to be completed.

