### **Continuing on Monotherapy**

If a patient discontinues osimertinib due to toxicity the patient may continue with savolitinib until progression.

If a patient discontinues savolitinib due to toxicity they may continue with osimertinib monotherapy until the Principal Investigator believes there is no further benefit (this may be beyond PD in the absence of clinical symptoms or signs indicating clinically significant PD; no decline in performance status; absence of rapid PD or threat to vital organs or critical anatomical sites [eg, central nervous system metastasis, respiratory failure due to tumour compression, spinal cord compression] requiring urgent alternative medical intervention; or no significant, unacceptable or irreversible toxicities related to study intervention), according to the SoAs ([Table 1](#) and [Table 2](#)).

Following PD, patients may continue on osimertinib monotherapy and continue with all safety assessments as per the SoAs ([Table 1](#) and [Table 2](#)). Savolitinib monotherapy (either if originally randomised to savolitinib plus placebo or after discontinuation of osimertinib if originally randomised to savolitinib plus osimertinib) post progression is not permitted.

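### The bans on savolitinib monotherapy after progression in Sections 4.1.1 and 7.1 do not except the cross-over interval, in which Section 4.1.2 and Table 2 say savolitinib should continue

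*Supplement*

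**What the plan says.** Four places in the protocol bear on savolitinib after progression.

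- **Section 4.1.1.** At progression the blind can be broken, and "patients who were initially randomised to the savolitinib plus placebo arm will be given the opportunity to cross-over", with a pointer to Sections 4.1.2 and 6.3. Later in the same paragraph, savolitinib monotherapy is allowed only up to RECIST progression, and this explicitly includes the placebo arm. The paragraph closes: "Savolitinib monotherapy post-progression is not permitted".
- **Section 7.1, under Continuing on Monotherapy.** The ban is restated. Its subject begins "Savolitinib monotherapy (either if originally randomised to savolitinib plus placebo" and goes on to cover combination-arm patients who have stopped osimertinib.
- **Section 4.1.2.** "Patients who cross-over must not receive any other anti-cancer therapies between the assessment of PD and the addition of osimertinib". Savolitinib is to be carried on without a break in that period. The time limit is: "Patients should be crossed over as soon as possible after the assessment of PD and within 28 days of their progression scan".
- **Table 2, footnote i.** It gives the same instruction: "Savolitinib treatment should continue uninterrupted during this period".

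The list of discontinuation reasons in Section 7.1 includes RECIST progression, but with the rider "unless the patient is randomised to savolitinib plus placebo, when cross-over to savolitinib plus osimertinib may be permitted".

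**The concern.** The bans and the cross-over rule give opposite dosing instructions for the same patients over the same days. The ban in Section 7.1 cannot be set aside as aimed at other patients, because it names the only arm that can cross over.

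What is at stake is conduct. A site that follows the bans stops savolitinib at progression and starts it again with osimertinib, and Section 4.1.2 allows no other anti-cancer therapy in between. A site that follows Section 4.1.2 departs from the wording of Sections 4.1.1 and 7.1, in a protocol whose Section 8 makes adherence essential and allows no waivers.

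**Working it through.** The plan states no figure to reproduce. The check is a comparison of texts, with one bound on numbers and one on time.

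**1. Is savolitinib in this interval savolitinib monotherapy?** Yes. Section 4.1.2, in its text on early termination, uses savolitinib monotherapy as another name for savolitinib plus placebo. Section 4.1.1 also counts the placebo arm as monotherapy.

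**2. Is the interval after progression?** Yes. Section 4.1.2 defines it as running from the assessment of progression to the addition of osimertinib.

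**3. Does either ban except it?** No. Two nearby texts come close:

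| Text | What it does | What it leaves open |
|---|---|---|
| Pointer to 4.1.2 and 6.3 in Section 4.1.1 | Is attached to the offer of cross-over | Does not qualify the closing ban |
| Rider on progression in the Section 7.1 list | Keeps progression from ending treatment where cross-over may be permitted | Says nothing of savolitinib alone before osimertinib starts; the ban that follows has no such rider |

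**4. Does the protocol make a gap likely?** It builds in steps. Under Section 6.3 the code is available "Once the investigator has documented progression in the eCRF, and obtained approval for unblinding from the study physician". Section 4.1.2 adds a separate signed consent form. Cross-over on the day of the progression assessment is possible, and then there is no interval and no conflict.

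**5. Who can be affected?** Only savolitinib plus placebo patients who cross over at progression with a gap. The planned arm size is 56 / 2 = 28. Section 9.2 says the planned number will not be reached, so the arm should be smaller than 28, and those who cross over with a gap fewer still. No actual count is given. The following are outside the conflict:

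- patients who cross over without progression after the study is unblinded;
- placebo-arm patients who do not cross over, for whom the ban stands;
- combination-arm patients who have stopped osimertinib, for whom the ban also stands.

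**6. How long can it last?** The limit is 28 days from the progression scan. The interval starts at the assessment of progression, so its length is at most 28 days less the time from scan to assessment. The documents do not give that time.

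**7. Which analyses does it reach?** Section 9.4.2.1 takes data for the ORR up to progression, so dosing after progression cannot change it. Section 9.4.2.3 has the cross-over endpoints summarised descriptively only.

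**The case against.** The best reply is that this is a general rule beside a specific one, and that the specific one governs. Section 4.1.2 is explicit, Table 2 repeats it, and Table 2 is the schedule that a site follows once a patient crosses over. Section 4.1.1 points to 4.1.2, and the progression item in Section 7.1 makes room for cross-over. The heading Continuing on Monotherapy suggests that the ban was written for patients staying on one agent, not for a short bridge to a combination already planned. Most of this stands. It settles what was intended and keeps the point minor. It does not put an exception into either sentence, and the Section 7.1 sentence is itself specific about the arm.

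A second reply is that a blinded site cannot apply a monotherapy ban before the code is broken. That is true of many patients but not all. A patient who has stopped the osimertinib/placebo tablet for toxicity is known to be on savolitinib alone without any code-break. After the study is unblinded under the current version, the arm is known for patients who stay on savolitinib monotherapy and later progress.

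A reader might go further and infer a safety hazard, because Appendix I 3.3 reports acute hypersensitivity mostly when savolitinib is restarted. The documents do not support that step. The appendix says that most hypersensitivity reactions came in the first six weeks of therapy, and it describes severe reactions on restart in some patients who had already had an initial reaction. Its restart procedure is triggered by interruption for toxicity or by hypersensitivity, not by a stop made for progression. No rate is given for a stop of that kind.

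**Conclusion.** The point holds as a minor error in a dosing rule: two sentences forbid, without exception, what Section 4.1.2 and Table 2 footnote i ask for. The intent is clear from Section 4.1.2.

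Its reach is small: fewer than 28 patients if the 1:1 allocation held as planned, over an interval that ends within 28 days of the progression scan. The effect on the primary ORR is none. It would be wrong to read into this a flaw in the design, a bias in an efficacy comparison, or a measured risk to patients. The documents give no count of affected patients, no typical length of the gap, and no safety rate for it. Nor do they show that any site has stopped savolitinib because of these sentences.

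**What to change.** Add one clause to the ban in Section 4.1.1 and the same clause to the ban in Section 7.1: *except, for patients randomised to savolitinib plus placebo who will cross over, between PD assessment and the start of osimertinib, within 28 days of the progression scan (Section 4.1.2)*.

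Keep the exception tied to that arm. A general sentence that blinded study treatment continues until the code is broken may look like a convenient addition, but it should not be made. It would let a combination-arm patient who has stopped osimertinib stay on savolitinib alone after progression, which Section 7.1 rightly forbids, and that patient has no cross-over to bridge to. Leave Appendix I 3.3 unchanged.

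The cost is one clause in two places, by amendment or by a clarification letter to sites. It needs no new assessment, no new data item and no change to any analysis.
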